6.3.3. Outcomes Research Endpoints

Outcomes Research Endpoints, also known as Patient-Reported Outcomes, are:

Patient Global Assessment of Arthritis, a value on the scale of 0 to 100 (a visual-analog score, VAS).

Patient Global Assessment of Pain, a VAS, scale of 0 to 100.

Health Assessment Questionnaire-Disability Index (HAQ-DI) is a total score based on items that query the patient on how well the patient can dress and groom self, arise from bed, eat during the day, walk, perform hygiene, reach, grip, and perform common daily activities. The HAQ-DI alone is analyzed, and is on the scale of 0 to 3.

SF-36 Health Survey (Version 2, Acute) has 36 items that are summarized into eight domain scores measuring Physical Functioning, Role Physical (physical life), Social Functioning, Bodily Pain, Mental Health, Role Emotional (emotional life), Vitality, and General Health: these in turn are summarized into two component scores: Mental, and Physical. These 8 domains and 2 scores are individually analyzed. They are scaled to be centered at 50, with a standard deviation of 10. Each domain score can also be expressed on the scale of 0 to 100.

Work Productivity and Activity Impairment (WPAI) has 6 items that measure four concepts: Absenteeism (percentage of time missed from work); Presenteeism (percentage of impairment experienced while at work); Work productivity loss (overall work impairment - the combination of absenteeism and presenteeism); and Activity impairment (the percentage of impairment in daily activities). The four scores are individually analyzed.

EuroQoL EQ-5D has five items for each of the domains Unusual Activities; Anxiety/Depression; Pain/Discomfort; Mobility; and, Self Care. These five are in turn summarized into a single utility score. There is also a EuroQol visual-analog score (EQ-VAS, 0 -100) anchored with 0 as the worst health you can imagine and 100 as the best health you can imagine. The scores are individually analyzed, and the utility score is analyzed as well.

The endpoints of interest are the actual values and the change from baseline values at each post-baseline scheduled visit including:

- Patient Assessment of Arthritis;
- Patient Global Assessment of Pain;
- HAQ-DI;
- SF-36 (each of the 8 domain scores (norm-based) and 2 component summary scores);
- WPAI (each of the four scores);
- EQ-5D (five domain scores and Utility Score) and EQ-VAS.

6.4. Covariates

The following demographic variables will be included as covariates in the multivariate Cox proportional hazard model:

Geographic regions:

4 levels: USA/Canada, Europe, Latin America, and rest of world.

Age:

In years (to the nearest year) at entry to the study (categorized as 50 to <65, 65 to <75, ≥ 75).

Smoking:

Current or ex-smoker, lifetime nonsmoker.

Gender:

Male and Female.

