4.1. Inclusion Criteria

Subject eligibility should be reviewed and documented by an appropriately qualified member of the investigator's study team before subjects are included in the study.

Subjects must meet all of the following inclusion criteria to be eligible for enrollment into the study:

1. Evidence of a personally signed and dated informed consent document indicating that the subject (or a legal representative) has been informed of all pertinent aspects of the study.
2. Must be at least 50 years of age or older.
3. Has moderate to severe rheumatoid arthritis inadequately controlled with methotrexate alone with a score of 6 or greater on the 2010 American College of Rheumatology/European League Against Rheumatism Classification Criteria for Rheumatoid Arthritis ([Appendix 1](#)).
4. Has ≥ 6 tender/painful joints on motion and ≥ 6 swollen joints (28 joint count).
5. Has a C-reactive protein measured by a high sensitivity assay (hs-CRP) ≥ 0.3 mg/dL in the central laboratory.

6. Meets Class I, II or III of the American College of Rheumatology (ACR) 1991 Revised Criteria for Global Functional Status in RA where usual self-care activities including dressing, feeding, bathing, grooming, and toileting; avocational (recreational and/or leisure) and vocational (work, school, homemaking) activities are subject-desired and age- and sex-specific.
 - Class I – Completely able to perform usual activities of daily living (self-care, vocational, and avocational).
 - Class II – Able to perform usual self-care and vocational activities, but limited in avocational activities.
 - Class III – Able to perform usual self-care activities, but limited in vocational and avocational activities.
7. Has taken methotrexate continuously for at least 4 months prior to the Screening visit and has taken a stable weekly dose of methotrexate with supplemental folic or folinic acid for at least 6 weeks prior to the Baseline visit.
 - Methotrexate doses less than 15 mg/week are allowed only in the presence of documented intolerance or toxicity from higher doses.
 - Doses higher than 25 mg/week are not permitted under any circumstances.
 - Folic acid doses should be at least 5 mg per week; folinic acid doses should be at least 2.5 mg per week.
8. Have at least one of the following cardiovascular risk factors at screening:
 - Current cigarette smoker.
 - Diagnosis of hypertension.
 - High density lipoprotein (HDL) <40 mg/dL.
 - Diabetes mellitus.

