 - Family history of premature coronary heart disease (CHD); the family history should be considered positive for premature CHD if clinical CHD or sudden death can be documented in a first degree male relative younger than 55 years of age or in a first degree female relative younger than 65 years of age.
 - Presence of extra-articular disease associated with rheumatoid arthritis, which may include nodules, Sjögren's syndrome, anemia of chronic disease and pulmonary manifestations.

- History of coronary artery disease including a history of revascularization procedure, coronary artery bypass grafting, myocardial infarction, cardiac arrest, unstable angina, acute coronary syndrome.
9. Subjects must be willing and able to comply with scheduled visits, treatment plan, laboratory tests, and other study procedures.
10. Male and female subjects of childbearing potential must agree to use a highly effective method of contraception throughout the study and for at least 28 days after the last dose of assigned treatment. A subject is of childbearing potential if, in the opinion of the investigator, he/she is biologically capable of having children and is sexually active. (For Canada, please refer to [Appendix 6](#) for specific contraception requirements).
11. Female subjects of childbearing potential must test negative for pregnancy.
12. Female subjects who are not of childbearing potential must meet at least one of the following criteria:
- Have undergone a documented hysterectomy and/or bilateral oophorectomy;
 - Have medically confirmed ovarian failure or;
 - Achieved postmenopausal status, defined as: cessation of regular menses for at least 12 consecutive months with no alternative pathological or physiological cause; and have a serum follicle-stimulation hormone (FSH) level within the laboratory's reference range for postmenopausal females.
13. Subjects must screen negative for active tuberculosis or inadequately treated tuberculosis infection (active or latent) as evidenced by the following:
- a. Negative QuantiFERON Gold[®]™ In-Tube test performed at screening:
- This is required unless the subject has been adequately treated for active or latent tuberculosis or a negative QuantiFERON Gold[®]™ In-Tube test was previously performed and documented within the 3 months prior to screening.

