9.2. Safety Analysis

9.2.1. Analysis of Primary Safety Endpoint

The co-primary safety endpoints of malignancies and MACE will be analyzed to provide comparative rates for tofacitinib vs. the combined TNFi.

The primary statistical safety objective is the estimation of the hazard ratios relative to the TNFi control for the two tofacitinib doses combined and for each dose of tofacitinib separately for the adjudicated events of MACE and malignancy excluding non-melanoma skin cancer. Analysis of the primary safety endpoints will be based upon adjudicated events.

Hazard ratios for the safety events of main interest will be calculated separately for each primary endpoint. The ratios for both tofacitinib doses combined versus the control, for each tofacitinib dose versus the control, and for the two tofacitinib doses versus each other will be reported along with their 95% confidence intervals. Adjustments for multiplicity will not be applied.

The primary statistical method for deriving estimators for hazard ratios will be the fitting of proportional hazards (Cox) regression models. A model containing only the single independent variable for treatment group will be calculated and reported. The effects of adding other predictors to the model, such as geographic region, age, gender, and so forth will be fully explored and reported. An analysis by TNFi subset strata (ie, the sites/regions where either adalimumab or etanercept was used) will be conducted to assure consistency of results.

A Surveillance, Epidemiology, and End Results (SEER) analysis of the malignancy endpoint will be conducted.

Both total time (or ITT) and on treatment analyses of the main safety endpoints will be conducted. The total time analysis will not censor times to event and will ascribe events to randomized treatment.

The on-treatment analysis for MACE will censor subjects who crossover from tofacitinib, adalimumab or etanercept to standard of care at 60 days after standard of care is initiated. The principal analysis for malignancies will not censor for subjects crossing to standard of care (ie, will be the total time analysis).

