8.1. Statistical Methods

8.1.1. Analyses of Time-to-Event Data

Comparisons of hazard functions in time-to-event analyses will be carried out via (linear) Cox proportional hazard models. Censoring conventions are given in [Section 7](#). A univariate analysis model containing only the single independent variable for treatment group will be calculated and reported.

In addition, the effects of adding other predictors to the Cox model, such as geographic region, age group, gender, and smoking status will be fully explored and reported.

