8.2.1. Primary Analysis

Safety endpoint analyses will be carried out using the data collected on the Safety Analysis Set.

Two methods in defining time to an event will be used for the co-primary time-to-event safety endpoints: 60-Day On-Treatment Time and Total Time (see [Section 7.1.1](#) for definitions). The 60-Day On-Treatment Time definition will be used for primary MACE analysis. The Total Time definition will be used for primary malignancies (excluding NMSC).

This primary objective will be addressed via the analysis of the times to these events by proportional hazard (Cox) models via univariate model analysis. See details in [Section 8.1.1](#).

In the time-to-event analyses using a Cox model, the treatment groups will be tofacitinib 5 mg BID, tofacitinib 10 mg BID, and TNFi regimen (adalimumab 40 mg QOW SC and etanercept 50 mg QW SC combined).

Ninety-five percent CIs for the hazard ratios for the combined tofacitinib regimens compared to the TNFi regimen as well as for the 3 pair-wise treatment comparisons, tofacitinib 10 mg BID vs. tofacitinib 5 mg BID, tofacitinib 5 mg BID vs. TNFi, tofacitinib 10 mg BID vs. TNFi, will be presented. For this analysis, only treatment group will be used as an independent variable in the model. For the Total Time analyses changes from original randomized treatment will be ignored. For the 60-Day On-Treatment Time analyses, rules for censoring times to event due to switching from randomized treatment to standard of care are given in [Section 7](#).

Further, multivariate analysis and analysis by TNFi subset strata (ie, the sites/regions where either adalimumab or etanercept was used, in other words, USA/Puerto Rico/Canada as one stratum, the rest as the other stratum) will be conducted to assure consistency of results. No additional analyses comparing adalimumab vs. etanercept will be conducted for the purpose of reporting the primary endpoints of the study; when reporting the primary endpoint analyses, any difference in hazard ratio between the two TNFi controls will be attributed to geographic difference.

These analyses will be used to check the robustness and to assure consistency of the results for primary safety endpoints:

- Models containing independent variable of treatment group adjusted with geographic region, age group, gender, and smoking status (see covariates in [Section 6.4](#)) will be fitted using Safety Analysis Set.

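### The supportive adjusted Cox models merge current with former smokers and leave out coronary history; finer coding is a low-cost improvement with a small expected effect

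*SAP*

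**What the plan says.** SAP 6.4 introduces its list with "The following demographic variables will be included as covariates in the multivariate Cox proportional hazard model". The list has four items: region (four levels), age (three bands), gender, and smoking, coded "Current or ex-smoker, lifetime nonsmoker". SAP 8.2.1 uses the same four for both co-primary endpoints in one of its robustness and consistency checks: "Models containing independent variable of treatment group adjusted with geographic region, age group, gender, and smoking status". No section names coronary disease, or any other cardiovascular history, as a Cox covariate.

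Two passages are worded more openly. SAP 8.1.1 refers to "the effects of adding other predictors to the Cox model, such as geographic region, age group, gender, and smoking status", and Protocol 9.2.1 to "The effects of adding other predictors to the model, such as geographic region, age, gender, and so forth". Neither names coronary history.

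Protocol 4.1, criterion 8, requires at least one of seven cardiovascular risk factors. One is "Current cigarette smoker", which does not cover former smokers. Another begins "History of coronary artery disease including a history of revascularization procedure" and goes on to include myocardial infarction. Protocol 6.1 takes smoking status at screening. SAP 6.2 lists cardiovascular risk and smoking history among the baseline characteristics to be summarised.

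The primary Cox model in SAP 8.2.1 contains treatment group only. The decision rules in SAP 4.2 rest on hazard ratios from that primary analysis.

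**The concern.** Protocol 5.1 states no stratification factor, so balance on smoking and coronary history is left to chance. An adjusted model removes the effect of an imbalance only in what it contains. If one arm has more current and fewer former smokers, while the share who ever smoked is the same, the two-level covariate has the same distribution in every arm and adjusts for nothing. The same applies to coronary history, which is absent altogether. Its definition in criterion 8 includes prior myocardial infarction, and MACE counts non-fatal myocardial infarction, so it is a natural predictor for that endpoint.

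What is at stake is how informative a pre-specified supportive analysis is, for MACE and for smoking-related cancers.

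**Working it through.** **1. The plan's own figures.** Protocol 9.1 asks for 138 malignancies (90% power) and 103 MACE (80% power) at margin 1.8, true hazard ratio 1.0. With the Schoenfeld formula and a 2/3 to 1/3 split:

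events = (z for two-sided 5% + z for power)² / [(2/3)(1/3)(ln 1.8)²]

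This gives 136.9 (137) and 102.2 (103), which agrees with the plan. The formula is for an unadjusted comparison, so the covariate list does not enter it.

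**2. Yardsticks.**
- SE of the MACE log hazard ratio at 103 events: 1/√(103 × 2/9) = 0.209. For malignancy at 138 events it is 0.181.
- Largest point estimate that still meets the 1.8 margin: 1.8 × exp(−1.96 × 0.209) = 1.20 at 103 events, and 1.26 at 138.

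**3. Smoking.** The documents give no prevalences or relative risks, so these are assumed: 25% current, 25% former, 50% never, with relative risks 2.5, 1.3 and 1. About 4000 subjects at 1:1:1 gives 2667 on combined tofacitinib and 1333 on TNFi.
- Average relative risk: 0.25 × 2.5 + 0.25 × 1.3 + 0.50 × 1 = 1.45.
- A shift of d from former to current in one group multiplies the hazard ratio by about 1 + d(2.5 − 1.3)/1.45.
- Chance SD of d, with the ever-smoker share fixed: √[(0.25 × 0.25/0.50)(1/2667 + 1/1333)] = 0.0119, or 1.19 points.
- 1 SD: 1 + 0.0119 × 1.2/1.45 = 1.010, which is about 5% of one MACE SE. 2 SD: 1.020.
- Larger shifts: 3 points gives 1.025 and 5 points gives 1.041, but these are 2.5 and 4.2 SD.

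The same formula over other assumed values:

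| Current / former share | Relative risk, current / former | 2-SD factor |
|---|---|---|
| 20% / 20% | 1.5 / 1.2 | 1.006 |
| 25% / 25% | 2.0 / 1.2 | 1.015 |
| 30% / 20% | 2.5 / 1.3 | 1.018 |
| 15% / 35% | 3.0 / 1.2 | 1.029 |

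**4. Coronary history (MACE).** Prevalence p and hazard ratio h are assumed: p = 5-20%, h = 1.5-4.
- Chance SD of the difference: √[p(1 − p)(1/2667 + 1/1333)].
- Shift in the log hazard ratio: (h − 1) × SD / [1 + p(h − 1)].
- Low end (p = 5%, h = 1.5): SD 0.0073, shift 0.0036, 2-SD factor 1.007.
- High end (p = 20%, h = 4): SD 0.0134, shift 0.0252, 2-SD factor 1.052.
- A 1-SD shift is therefore about 2% to 12% of one SE.

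**5. Parameters after the change.** MACE: treatment 2, region 3, age 2, gender 1, smoking 2, coronary history 1, total 11; 103/11 = 9.4 events per parameter, against 103/9 = 11.4 under the current list. Malignancy, without the coronary term: 138/10 = 13.8.

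**The case against.** The strongest reply is that nothing depends on this model. It is one of three robustness and consistency checks in SAP 8.2.1, alongside the TNFi strata and the Per Protocol set, and it has no pass criterion. The decision uses the treatment-only model, and randomization protects that comparison from baseline imbalance in expectation. All of this stands.

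The open wording in SAP 8.1.1 and Protocol 9.2.1 also leaves room to add predictors. That stands in part: coronary history may be explored, but it is not pre-specified, and in an open-label trial a covariate chosen after results are known carries less weight. Baseline tables would show an imbalance but not adjust for it.

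The smoking illustration puts the whole shift inside the ever-smoker group. An imbalance between ever and never smokers would still be adjusted for, at least partly.

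Picking coronary disease leaves hypertension, diabetes, low HDL, family history and extra-articular disease outside the model. That is a fair observation. Coronary history is the listed factor closest to the MACE components, and one term is what 103 events can reasonably carry.

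No case report form is shown, so a separate coronary-history field is inferred from the criterion 8 check and the medical history.

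**Conclusion.** The point holds as an optional refinement of a supportive analysis. The pre-specified models cannot adjust for a current/former smoking imbalance or, for MACE, for coronary history. Under the assumed inputs, a 2-SD chance imbalance moves the hazard ratio by about 0.6-2.9% for smoking and 0.7-5% for coronary history. That could matter only for an estimate already close to about 1.20 (MACE) or 1.26 (malignancy).

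A reader might infer that the primary hazard ratio is biased, or that the plan relies on this model to rule out baseline imbalance. The documents support neither: the primary model is unadjusted, and the stated purpose is robustness and consistency.

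A reader might also suspect that selective stopping in the on-treatment MACE analysis makes the omission serious. The trial is open-label and Protocol 13.7 expects about 15% annual discontinuation of assigned treatment, but nothing shows that stopping depends on coronary history or smoking and differs by arm.

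**What to change.** In SAP 6.4, code smoking as current, former and never. Add history of coronary artery disease (yes/no, from the criterion 8 and medical history data) as a covariate for the adjusted MACE model only. Mirror both changes in SAP 8.2.1. Keep the unadjusted model as primary.

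The cost is a few lines of SAP text and a check that both items can be derived from the baseline data for every subject. The decision rule, event targets and power do not change. The one statistical cost is the drop to about 9.4 events per parameter for MACE. Fitting the combined-dose comparison with a single treatment term brings this to 103/10 = 10.3. The herpes zoster model in SAP 8.2.2 also uses smoking status, so the SAP should say whether the three-level coding applies there too.

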7. HANDLING OF MISSING VALUES

7.1. Safety Data

Missing values for safety endpoints will not be imputed.

7.1.1. Censoring Time for Time-to-event

There are three ways in defining the time to an event:

- The “60-Day On-Treatment Time” is the time from first study dose to an event observed while a subject is exposed to the study treatment plus the applicable attribution window. The 60-Day On-Treatment Time analysis will censor subjects who cross over from tofacitinib or TNFi to standard of care at 60 days after the last dose of randomized study drug.
- The “Total Time” is the time from first study dose to an event regardless whether the event occurs during on-treatment period or after the subject discontinues the study treatment and is still being followed. The Total Time analysis will not censor subjects who cross over from tofacitinib or TNFi to standard of care and will ascribe events to randomized treatments.
- The “28-Day On-Treatment Time” is the time from first study dose to an event observed while a subject is exposed to the study treatment plus the applicable attribution window. The 28-Day On-Treatment Time analysis will censor subjects who cross over from tofacitinib or TNFi to standard of care at 28 days after the last dose of randomized study drug.

More specifically, in time-to-event analyses for a given event, a subject’s time to event will be considered censored if any of the following conditions occurs prior to the subject experiencing the event in question:

- The subject is lost to follow-up (censoring time = study day of last on-study contact, eg, last visit, last lab test, and the like).
- The subject withdraws consent (censoring time = study day of last on-study contact).
- The subject is in the study under the protocol at the declared end of the study (censoring time = study day of last on-study contact).
- The subject dies without having experienced the event of interest (censoring time = study day of death).

For the **60-Day On-Treatment Time Analyses** of time-to-event, in addition to the foregoing, when a subject changes from the randomized study treatment to standard of care, the subject’s time to event will be considered censored (censoring time = last dose day of randomized study regimen + the attribution window, or the study day of last on-study contact, whichever is earlier). It will be used for the primary safety endpoint MACE but excluding malignancy (excluding Non-melanoma Skin Cancer (NMSC)), and the attribution window will be 60 days. In other words, the censoring time will be the earliest of study day of last on-study contact, study day of death, and last dose day of randomized study regimen plus 60 days.

For the **Total Time Analyses** of time-to-event, the censoring time will follow the four foregoing listed cases, ie, the censoring time will not change when a subject changes from the randomized study treatment to standard of care. In other words, the censoring time will be the earlier of study day of last on-study contact and study day of death.

For the **28-Day On-Treatment Time Analyses** of time-to-event, in addition to the foregoing, when a subject changes from the randomized study treatment to standard of care, the subject's time to event will be considered censored (censoring time = last dose day of randomized study regimen + the attribution window, or the study day of last on-study contact, whichever is earlier). It will be used for all the secondary safety endpoints, and the attribution window will be 28 days. In other words, the censoring time will be the earliest of study day of last on-study contact, study day of death, and last dose day of randomized study regimen plus 28 days.

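### SAP 7.1.1 gives two conflicting ends of follow-up, and its switch rule can censor a fatal event before it occurs inside the 60- or 28-day window

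*SAP*

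**What the plan says.** SAP 7.1.1 has two layers.

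The first layer gives definitions and a list of four cases. A time is "considered censored if any of the following conditions occurs prior to the subject experiencing the event in question". For loss to follow-up the rule is "censoring time = study day of last on-study contact, eg, last visit, last lab test, and the like". Consent withdrawal and end of study also use last contact; the latter reads "The subject is in the study under the protocol at the declared end of the study (censoring time = study day of last on-study contact". Death has its own rule: "The subject dies without having experienced the event of interest (censoring time = study day of death". The definitions of the two on-treatment clocks count events during exposure plus an attribution window. They censor a crossover 60 or 28 days after the last dose of randomized drug, with no mention of last contact.

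The second layer restates the rule for each clock. The Total Time paragraph says that "the censoring time will follow the four foregoing listed cases" and concludes: "In other words, the censoring time will be the earlier of study day of last on-study contact and study day of death". In both on-treatment paragraphs, a subject who switches to standard of care is censored at "last dose day of randomized study regimen + the attribution window, or the study day of last on-study contact, whichever is earlier". Both then summarise: "the censoring time will be the earliest of study day of last on-study contact, study day of death", and last dose plus 60 or 28 days.

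Under SAP 8.2.1 the 60-day clock is primary for MACE and Total Time is primary for malignancy. Under 7.1.1 and 8.2.2 the 28-day clock serves the secondary endpoints, including all-cause mortality. SAP 8.1.2, on incidence rates, uses time to first event for subjects with events and the 7.1.1 censoring time for those without.

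**The concern.** The restatement is offered as a paraphrase of the list, but the two agree only if the last contact is never earlier than the death. The section's examples of contact are a visit and a laboratory test, and these normally come before a death. The minimum then picks the last contact, and the separate rule for deaths has no effect.

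The on-treatment paragraphs matter more. Their switch rule can end the risk window at the last visit, although the definition runs it to 60 or 28 days after last dose. Survivors usually have a later contact, so the cap bears mainly on subjects who die. It is not confined to them: a non-fatal event after the last recorded contact of a subject who is then lost would meet the same cap. Cardiovascular death is part of MACE (SAP 6.2), and MACE is tested against margins of 1.8 and 2.0 (SAP 4.2). Whether a fatal event counts should not depend on which of two sentences a programmer follows.

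**Working it through.** **Step 1. Apply both layers to example records** (illustrative days; contact taken as the last visit).

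| Record | List and definitions | Restatement and switch rule |
|---|---|---|
| A. On drug to Day 500, last visit Day 450, sudden cardiac death Day 500 | No listed condition precedes the event: MACE at Day 500 | min(450, 500, 560) = 450, but this is a censoring time and the subject has an event |
| B. Last dose Day 440, switched, last visit Day 450, fatal MI Day 490 | Window runs to 440 + 60 = 500: MACE at Day 490 | Switch rule: min(500, 450) = 450; the event comes 40 days later and is lost |
| B′. As B, 28-day clock, death Day 460 | Window runs to 440 + 28 = 468: death at Day 460 | min(468, 450) = 450; the death is lost |
| C. On drug to Day 500, last visit Day 450, non-cardiovascular death Day 500, no MACE | Censored at Day 500 | min(450, 500, 560) = 450 |

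C is a direct contradiction between the layers. In B and B′ the switch comes before the event, so the condition for censoring is met and the cap applies as written. A is not lost unless the restatement is used as a cut-off on events.

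**Step 2. Size of C.** Share of person-time lost = deaths without the event per 100 patient-years × mean gap in days / 365.25. The documents give neither input. Assumed ranges are 0.3 to 2.0 deaths and 45 to 135 days (visits are 90 days apart, SAP Appendix 1.1).
- Low: 0.3 × 45 / 365.25 = 0.04%.
- High: 2.0 × 135 / 365.25 = 0.74%.

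**Step 3. Rough size of B for MACE.** Protocol 13.7 expects about 15% of subjects to stop assigned treatment each year. Window time per year on drug = 0.15 × 60 / 365.25 = 0.0246, which is 0.0246 / 1.0246 = 2.4% of time at risk. If the hazard is the same in the window as on drug, 103 × 0.024 ≈ 2.5 of the 103 planned MACE fall there. With an assumed fatal share of 20% to 40%, that is about 0.5 to 1.0 fatal events, of which only those after the last contact are lost. A higher hazard just after stopping would raise this in proportion.

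**Step 4. Worst case, if the restatement is used as a cut-off.** First the plan's own figure (Protocol 9.1: margin 1.8, true hazard ratio 1.0, two-sided 95%; 1:1:1 randomization gives 2:1 for combined tofacitinib against TNFi):
- Events = (z₀.₉₇₅ + z_power)² / [(1/3)(2/3)(ln 1.8)²]. At 80% power this is 102.2, so 103, against 103 stated. At 90% it is 136.9, so 137, against 138 stated.
- Power = Φ(ln 1.8 × √(d × 2/9) − 1.96). At d = 103 it is 0.803.

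Then remove every fatal MACE:

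| Assumed fatal share | Events left of 103 | Power |
|---|---|---|
| 10% | 92.7 | 0.76 |
| 20% | 82.4 | 0.71 |
| 30% | 72.1 | 0.65 |
| 40% | 61.8 | 0.59 |

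The trial could run on to 103 counted events and regain the power, but the fatal events would still be missing.

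**Step 5. Direction.** If the fatal share differs by arm, the MACE hazard ratio is multiplied by about (1 − f_T) / (1 − f_C). With 30% on tofacitinib and 20% on control this is 0.70 / 0.80 = 0.875; with the shares reversed it is 0.80 / 0.70 = 1.143. Either direction is possible.

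**The case against.** The strongest reply is that censoring times are for subjects without events. SAP 7.1.1 censors only when a condition comes before the event, SAP 8.1.2 uses event time for subjects with events, and Protocol 9.1 says the final analysis uses all observed events. This stands for on-drug deaths (record A). It does not settle record B, where the switch precedes the event and the written cap gives an earlier day.

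A second reply is that the cap is loose wording for subjects with no event in the window, since the definition and the 60-day MACE attribution in 8.1.2 both look past the last dose. That may well be the intent, but the text does not say so.

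A third is that the examples of contact are open-ended, and Protocol 6.2 and 6.7 ask sites to document outcome. If a report made on or after the day of death counts as contact, the minimum returns the day of death and the conflict disappears. The SAP never says that it counts.

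A reader might infer more: that all cardiovascular deaths between visits leave the MACE analysis, that most deaths leave the mortality analysis, and that hazard ratios are pulled toward 1. The documents do not support this. No sentence discards an event for falling after the last contact of a subject still on drug. The list's rule for deaths covers only deaths without the event, so it does not time a fatal MACE, nor a death when death is the endpoint. The data safety monitoring board's message (Protocol 1.2) concerned pulmonary embolism and all-cause mortality on 10 mg BID. It did not report cardiovascular death as such, and pulmonary embolism death is excluded from MACE.

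**Conclusion.** The section contradicts itself and should be corrected, but the effect is modest. It is certain that the restated minimum and the list disagree whenever last contact precedes death. It is also certain that the switch rule, read literally with contact as a visit or laboratory test, censors an in-window fatal event before it occurs, contrary to the on-treatment definitions. The first effect is well under 1% of person-time on the assumed inputs. The second is about one primary MACE or fewer on the rough count above, which assumes a constant hazard and a fatal share of 20% to 40%. The power figures of 0.71, 0.65 and 0.59 describe a programming risk with an assumed fatal share; they do not follow from the SAP as written. The direction of any bias in the hazard ratio is not established.

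**What to change.** In all three clock paragraphs of SAP 7.1.1 (60-day for primary MACE, Total Time for malignancy, 28-day for secondary endpoints including mortality), delete the *In other words* sentences and the *whichever is earlier* brackets. Put in their place:

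- End of follow-up is the study day of death for a subject who dies while on study; otherwise it is the study day of last on-study contact.
- Total Time censors at end of follow-up.
- On-Treatment Time censors at the earlier of end of follow-up and last dose of randomized drug plus 60 (or 28) days.
- An adjudicated event, including a fatal one, on or before that day counts on its event date, even if it falls after the last visit.

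The cost is SAP wording and one derivation line before database release. No new data are needed.
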